4.4 Interim Analyses and Data Monitoring

The Independent Data Monitoring Committee (IDMC) will monitor the study for greater than expected efficacy and for safety. There will be one formal pre-planned interim analysis to assess greater than expected efficacy, which will be performed when approximately 67% of the planned primary efficacy outcome events (~680) have accrued and are adjudicated. Based on that analysis, the study may be stopped early, if there is overwhelming superiority of rivaroxaban ($p<0.001$, 2-sided) for the primary efficacy endpoint (following the Haybittle-Peto approach) ([Haybittle 1971](#)). Details on the approach to the interim analyses and refinement of decision rules are specified in the IDMC charter.

4.5 Data Rules

4.5.1 Analysis Dates

For the study, the following date and time window are of relevance for the analysis:

- Efficacy cut-off date:
The trial is designed to be terminated when 1015 patients have experienced a confirmed primary efficacy outcome event. The ECOD is a predicted common date when at least 1015 primary efficacy outcomes are expected to have occurred. It is the last calendar date acceptable for counting events for the primary analysis.
- Trial close-out window:
The time period when all subjects return to the clinic for an EOT visit. All randomized subjects should return for their EOT visit after the ECOD.

For each subject, the following individual dates are of relevance for analysis:

- Randomization date:
The date of randomization as recorded in the IxRS system.
- EOT Visit date:
The date of the EOT visit. If subjects do not have an EOT visit, the date will be missing.
- Date of last contact:
The date of the last documented contact with the subject or a third party (including data on subject survival status, see [Appendix A](#) for details).
- Date of first dose of study treatment:
The date of the first dose of rivaroxaban or rivaroxaban placebo, defined as:
 - Date of first dose from the appropriate CRF page capturing the study medication (rivaroxaban or rivaroxaban placebo) if this date is complete.
 - Date of the earliest logically possible dose of study medication (rivaroxaban or rivaroxaban placebo) administration in cases where the date of first dose is missing or incomplete. See [Appendix D](#) for details of the imputation rules.
- Date of last dose of study treatment:

Statistical Analysis Plan

Protocol No.: **BAY 59-7939 / 17454**

Page: 11 of 36

The date of the last dose of rivaroxaban or rivaroxaban placebo, defined as:

- Date of last dose from the appropriate CRF page capturing the study medication (rivaroxaban or rivaroxaban placebo) if this date is complete.
- Date of the latest logically possible dose of study medication (rivaroxaban or rivaroxaban placebo) administration in cases where the date of last dose is missing or incomplete. See [Appendix D](#) for details of the imputation rules.

4.5.2 Data Scopes

All analyses are based on two elements:

- 1) *analysis set*, which specifies which subjects will be included in an analysis; and
- 2) *data scope*, which specifies the time window within which data will be included in an analysis.

This section describes the coverage of the event *data scopes* used for the statistical analyses. *Analysis sets* are described in Section 5.

Data scope according to intention-to-treat principle (ITT)

The ITT data scope includes outcome events observed from randomization date until the ECOD. Events occurring after the ECOD will not be counted for primary analysis. This ITT data scope will be applied mainly to the analyses of efficacy variables.

Data scope according to treatment (on-treatment)

The on-treatment data scope will include all outcome events observed from randomization until 2 days following permanent discontinuation of the study drug. This on-treatment data scope will be applied mainly to the analyses of safety variables (e.g. bleeding).

Data scope according to overall study duration for sensitivity analysis

The overall study duration data scope will include all outcome events observed from randomization until the last contact/visit. This data scope will be applied for sensitivity analysis only.

4.5.3 Censoring rules for time-to-event variables

All efforts will be made to collect complete data for all subjects randomized in this study including visits by telephone contact.

Censoring rules for analyses according to the ITT principle

The censoring rule for time to first event analyses depends on the type of endpoint, thereby distinguishing between clinical events endpoints (primary efficacy composite and component, secondary efficacy and bleeding events) and CV-death / all-cause mortality.

Statistical Analysis Plan

Protocol No.: **BAY 59-7939 / 17454**

Page: 12 of 36

	Primary efficacy composite and components other than CV-death	All-cause mortality, CV-death
If the subject was randomized but has no post-randomization clinical event ascertainment date the subject will be censored :	At the randomization date + 1 day	Earlier of last contact alive date or ECOD If no last contact alive date, use the randomization date +1 day
Else, if the subject has withdrawn from the study but objected to further data collection the subject will be censored :	At the earlier date of the last clinical event ascertainment date (LCEAD), date of objection to further data collection or ECOD	Earlier of last contact alive date from public sources or ECOD If no last contact alive date from public sources, use the earlier date objection to further data collection or ECOD
Otherwise, the subject will be censored :	At the earlier date of last clinical event ascertainment date, date when patient died or ECOD	At the earlier date of last contact alive date or ECOD

Censoring rules for analyses according to the on-treatment principle

For on-treatment analyses (primary analysis for time to bleeding events, sensitivity analysis for primary efficacy endpoint and all secondary efficacy endpoints), patient with at least one dose of study medication and without documentation of an event within the on-treatment data scope will be censored similarly to the ITT data scope except that the date of last dose of study treatment + 2 days will be used as the cap for the time scope instead of ECOD.

Censoring rules for analyses according to the overall study duration principle

Above censoring rules for ITT data scope apply except that the date of last clinical event ascertainment or last contact alive will be used as the cap for the time scope instead of ECOD.

See [Appendix A](#) for additional details.

4.6 Determination of sample size

The study is event-driven and it is estimated that approximately 6,500 patients (3,250 per treatment group) need to be randomized in order to have 1,015 patients experiencing a confirmed primary efficacy outcome event. This number of events will allow the demonstration of superiority of rivaroxaban compared to placebo with regard to the primary outcome with a power of 90% and a one-sided level of significance $\alpha=0.025$ under the following assumptions:

- The effect size (Hazard Ratio (HR)) for rivaroxaban plus ASA vs. ASA alone is $HR=0.80$.
- The annualized event rate in the control arm is approximately 7.5% per year.
- The rate of patients with permanent discontinuation of study drug (rivaroxaban plus ASA switching to ASA alone or an equally effective treatment regimen) is approximately 5.5% 1st year, 8% 2nd year, 12% 3rd year (4% 1st half year + 8% 2nd half year), and 8% every half year afterwards.

Statistical Analysis Plan

Protocol No.: **BAY 59-7939 / 17454**

Page: 13 of 36

- The rate of patients lost to follow-up or with non-CV death is approximately 1.5% per year.
- The duration of the enrollment period is 18 months (approximately 15% 1st 6 months, 30% 2nd 6 months, 55% 3rd 6 months) and 2 years of follow-up from last patient-randomized until the ECOD.

The number of patients enrolled may be adjusted and the study duration may be adapted based on a blinded review of the observed overall event rate of confirmed primary efficacy outcomes during the study.

Sample size estimation was based on PASS 11 ([Hintze 2011](#)).

5. Analysis Sets

5.1 Assignment of analysis sets

All subjects who have been randomized in the study are valid for assignment to analysis sets.

5.1.1 Intention-to-treat (ITT) analysis set

The intention-to-treat analysis set, also termed full analysis set in the International Conference on Harmonization (ICH) E9 guideline, will include all randomized subjects. Subjects will be categorized to the treatment group to which they were assigned by the IxRS; i.e., they will be analyzed as randomized.

5.1.2 Safety analysis set (SAF)

The SAF will include all randomized subjects who received at least one dose of study medication (rivaroxaban or rivaroxaban placebo). Subjects will be categorized to the group to which they were assigned by the IxRS unless the incorrect treatment was received throughout the study. In this case, subjects will be analyzed for safety as actually treated.

The planned analyses for the primary and secondary efficacy and safety variables are summarized in but not limited to Table 1 below

Statistical Analysis Plan

Protocol No.: **BAY 59-7939 / 17454**

Page: 14 of 36

Table 1 Sketch of the planned primary and secondary efficacy and safety analyses

Endpoint	Analysis Type	Analysis Set (population) ¹	Data Scope ²	Censoring Rule ³	Analysis Method
Efficacy					
Primary					
Composite of MI, ischemic stroke, CV death, Acute Limb Ischemia, major amputation due to a vascular etiology	Main	ITT	ITT	ITT	Stratified log-rank test, HR estimates from stratified Cox PH model, KM plot
	Sensitivity	ITT	ITT	ITT	Cox PH model with no stratification ; Cox PH model with actual stratification ; robust proportional hazard estimator; tipping point analysis
		SAF	On-treatment	On-treatment	Stratified log-rank test, HR estimates from stratified Cox PH model, KM plot
		ITT	Overall study duration	Overall study duration	Stratified log-rank test, HR estimates from stratified Cox PH model, KM plot
	Subgroup	ITT	ITT	ITT	HR estimates from stratified Cox PH model ⁴ , forest plot
		SAF	On-treatment	On-treatment	HR estimates from stratified Cox PH model ⁴ , forest plot
Secondary					
All secondary efficacy variables. For the list of secondary efficacy variables, see section 6.2.2.	Main	ITT	ITT	ITT	Stratified log-rank test, HR estimates from stratified Cox PH model, KM plot
	Sensitivity	SAF	On-treatment	On-treatment	Stratified log-rank test, HR estimates from stratified Cox PH model, KM plot

Statistical Analysis Plan

Protocol No.: **BAY 59-7939 / 17454**

Page: 15 of 36

Endpoint	Analysis Type	Analysis Set (population) ¹	Data Scope ²	Censoring Rule ³	Analysis Method
Safety					
Primary					
TIMI major bleeding	Main	SAF	On-treatment	On-treatment	Stratified Cox PH model, KM plot
	Supportive	SAF	ITT	ITT	Stratified Cox PH model, KM plot
		SAF	Overall study duration	Overall study duration	Stratified Cox PH model, KM plot
	Subgroup	SAF	On-treatment	On-treatment	Stratified Cox PH model ⁴ , forest plot
Secondary					
ISTH major bleeding BARC type 3b and above bleeding	Main	SAF	On-treatment	On-treatment	Stratified Cox PH model, KM plot

Note: Details of the planned analyses are provided in section 6.

1. Intention-to-treat (ITT) analysis set – all randomized subjects. Treatment assigned as randomized; Safety analysis set (SAF) – all randomized subjects who received at least one dose of study medication. Treatment assigned as treated. See section 5.1 for details.
2. ITT data scope – all outcome events observed from randomization until efficacy cut-off date; On-treatment data scope – all outcome events observed from randomization until 2 days following permanent discontinuation of the study drug (rivaroxaban or rivaroxaban placebo). See section 4.5.2 for details. Overall study duration scope - all outcome events observed post randomization including post-study treatment follow-up.
3. See section 4.5.3 and [Appendix A](#) for details regarding the censoring rules according to each data scope.
4. Not stratified for subgroups related to type of procedure and clopidogrel use. See sections 6.2.4, 6.2.9 and 6.4.5 for details.

6. Statistical Methodology

6.1 Population characteristics

6.1.1 Disposition

The following will be tabulated overall and/or by treatment group:

- Study sample sizes (All enrolled subjects, ITT, and SAF)
- Study sample sizes by region, country, and site
- Subject disposition
- Number of subjects and primary reasons for screening failures (only overall)
- Number of subjects and primary reasons for permanent discontinuation of study medication (by treatment group and overall for ITT and SAF)
- Number of subjects and primary reasons for discontinuation from intended study treatment period (by treatment group and overall for ITT and SAF)

6.1.2 Demographics

The following demographic and baseline characteristics will be summarized by treatment group and overall in ITT and SAF. Summary statistics will be presented for metric variables. Frequency tables will be presented for categorical variables. Subjects will be considered fragile if age >75 years or weight ≤ 50 kg or baseline eGFR <50 mL/min.

- Age (<55; ≥ 55 to <65; ≥ 65 to ≤ 75 ; >75 years)

Statistical Analysis Plan

Protocol No.: **BAY 59-7939 / 17454**

Page: 16 of 36

- Age (<65; \geq 65 to <75; \geq 75 years)
- Age (<65; \geq 65 to <85; \geq 85 years)
- Sex (male, female)
- Race (White; Black or African American; Asian; American Indian or Alaska Native; Native Hawaiian or Other Pacific Islander; Not reported; Multiple)
- Type of qualifying procedure and clopidogrel use, per IxRS assignment (surgical; endovascular with clopidogrel; endovascular without clopidogrel)
- Qualifying revascularization procedure per IxRS (surgical; endovascular)
- Geographic Region (North America, Western Europe, Eastern Europe, Asia Pacific, South America, see [Appendix B](#) for details)
- Geographic Region (US, non-US)
- Weight (\leq 60 kg; >60 kg)
- estimated Glomerular Filtration Rate (eGFR) ($<$ 60 ml/min/1.73m², \geq 60 ml/min/1.73m²)
- eGFR ($<$ 15 ml/min/1.73m², \geq 15 to <30 ml/min/1.73m², \geq 30 to <60 ml/min/1.73m², \geq 60 ml/min/1.73m²)
- eGFR ($<$ 30 ml/min/1.73m², \geq 30 to \leq 50 ml/min/1.73m², $>$ 50 to \leq 80 ml/min/1.73m², $>$ 80 ml/min/1.73m²)
- Fragile subjects (yes, no)
- Qualifying revascularization procedure, actual (surgical; endovascular including hybrid)
- Clopidogrel use in relation to qualifying revascularization procedure (yes, no)
- Time from qualifying revascularization procedure to randomization, actual (\leq median, $>$ median)
- Type of qualifying procedure and clopidogrel use, actual (surgical; endovascular including hybrid with clopidogrel; endovascular including hybrid without clopidogrel)
- Clopidogrel use continued after randomization (none, \leq 30 days, $>$ 30 days)
- Prior coronary artery disease (CAD) (yes; no)
- Prior MI (yes; no)
- Prior limb revascularization (yes; no)
- Carotid artery disease history (yes; no)
- Critical limb ischemia (yes; no)
- Intermittent claudication present within past 12 months (yes; no)
- History of heart failure (yes; no)
- Classification of heart failure (NYHA class I, class II, class III, class IV)

Statistical Analysis Plan

Protocol No.: **BAY 59-7939 / 17454**

Page: 17 of 36

- Diabetes mellitus (yes; no)
- Smoking status (former, never, current)
- Hypertension (yes; no)
- Hyperlipidemia (yes; no)
- Baseline Ankle Brachial Index (ABI) (at Month 1 visit) (≤ 0.80 ; > 0.80)
- Baseline Toe Brachial Index (TBI) (at Month 1 visit) (≤ 0.60 ; > 0.60)

In addition, age, days from actual qualifying revascularization procedure to randomization and baseline Low-density lipoprotein (LDL) will be treated as continuous variable and summarized descriptively. Other baseline characteristics may be added.

6.1.3 Medical history

Medical history will be presented by the pre-specified terms as listed in the CRF. Medical history data will be evaluated by frequency tables, showing the number of subjects with medical history findings (i.e., listed conditions of previous diagnoses, diseases, or surgeries based on the CRF) that started before signing of the informed consent and that are considered relevant to the study.

6.1.4 Protocol Deviations

A summary of protocol deviations related to in- and exclusion criteria will be given by frequency tables. The summary will be based on ITT.

6.1.5 Prior and Concomitant Medications

Prior and concomitant medications will be presented by the pre-specified terms as listed in the CRF. Frequency tables by type of medication will be provided for prior medications prior to randomization and for concomitant medication post-randomization. The summaries will be by treatment group and overall based on ITT.

6.1.6 Extent of Exposure and Compliance

All summaries related to intake of study medication (rivaroxaban or rivaroxaban placebo) will be by treatment group based on SAF.

The treatment duration (date of last study medication- date of first study medication+1 day) will be summarized descriptively. Additionally the number of subjects by treatment duration category will be given (≤ 3 months, $>3-\leq 6$ months, $>6-\leq 9$ months, $>9-\leq 12$ months, $>12-\leq 18$ months, $>18-\leq 24$ months, >24 months).

The time on study medication (treatment duration excluding days off study medication) will be calculated and summarized descriptively.

The number of tablets taken will be summarized descriptively, as well as corresponding extent of exposure (number of tablets taken*dose).

Compliance (or adherence, defined as $100 * \text{number of tablets taken} / \text{number of tablets planned}$) will be presented by visit as entered in the CRF and summarized for the whole study. The number of subjects with at least 80% compliance will be presented.

Statistical Analysis Plan

Protocol No.: **BAY 59-7939 / 17454**

Page: 18 of 36

6.2 Efficacy

6.2.1 Primary efficacy variable

The primary efficacy variable is the time from randomization to first occurrence of any of the components of the composite outcome, including:

- MI
- ischemic stroke
- CV death
- ALI
- major amputation due to a vascular etiology

6.2.2 Secondary efficacy variables

The secondary efficacy variables of this study are:

- time from randomization to the first occurrence of MI, ischemic stroke, coronary heart disease mortality, ALI, and major amputation of a vascular etiology
- time from randomization to the first occurrence of an unplanned index limb revascularization for recurrent limb ischemia (subsequent index leg revascularization that was not planned or considered as part of the initial treatment plan at the time of randomization)
- time from randomization to the first occurrence of hospitalization for a coronary or peripheral cause (either lower limb) of a thrombotic nature
- time from randomization to the first occurrence of MI, ischemic stroke, all-cause mortality, ALI, and major amputation of a vascular etiology
- time from randomization to the first occurrence of MI, all-cause stroke, CV death, ALI, and major amputation of a vascular etiology
- time from randomization to the first occurrence of all-cause mortality
- time from randomization to the first occurrence of VTE events

6.2.3 Other efficacy variables

The other efficacy variables of this study are:

- time from randomization to the first occurrence of all subsequent limb revascularizations of the lower extremity that were not planned or considered as part of the initial treatment plan at the time of randomization.
- time from randomization to the first occurrence of all-cause amputations;
- patient reported outcomes using disease and non-disease specific questionnaires (European Quality of Life-5 Dimensions questionnaire (EQ-5D) and Walking Impairment Questionnaire (WIQ)).
- serial changes in limb hemodynamics (ABI and TBI).

Statistical Analysis Plan

6.2.4 Subgroup variables

The following subgroup analyses based on baseline and demographic characteristics are planned for the treatment comparisons of the primary efficacy and safety outcomes:

- Age (<55; \geq 55 to <65; \geq 65 to \leq 75; $>$ 75 years)
- Age (<65; \geq 65 to <75; \geq 75 years)
- Age (<65; \geq 65 to <85; \geq 85 years)
- Sex (male; female)
- Race (White; Black or African American; Asian; Other)
- Type of qualifying procedure and clopidogrel use, per IxRS assignment: (surgical; endovascular with clopidogrel; endovascular without clopidogrel)
- Qualifying revascularization procedure per IxRS (surgical; endovascular)
- Geographic Region (North America; Western Europe; Eastern Europe; Asia Pacific; South America, see [Appendix B](#) for details)
- Geographic Region (US, non-US)
- Weight (\leq 60 kg; $>$ 60 kg)
- estimated Glomerular Filtration Rate (eGFR) (<60 ml/min/1.73m², \geq 60 ml/min/1.73m²)
- eGFR (<15 ml/min/1.73m², \geq 15 to <30 ml/min/1.73m², \geq 30 to <60 ml/min/1.73m², \geq 60 ml/min/1.73m²)
- eGFR (<30 ml/min/1.73m², \geq 30 to \leq 50 ml/min/1.73m², $>$ 50 to \leq 80 ml/min/1.73m², $>$ 80 ml/min/1.73m²)
- Fragile subjects (yes, no)
- Qualifying revascularization procedure, actual (surgical; endovascular including hybrid)
- Clopidogrel use in relation to qualifying revascularization procedure (yes, no)
- Type of qualifying procedure and clopidogrel use, actual (surgical; endovascular including hybrid with clopidogrel; endovascular including hybrid without clopidogrel)
- Clopidogrel use continued after randomization (<30 days, \geq 30 days, none)
- Prior coronary artery disease (CAD) (yes; no)
- Prior MI (yes; no)
- Prior MI and age < 65 years (yes, no)
- Prior MI and reduced renal function, i.e., eGFR <60 mL/min (yes, no)
- Carotid artery disease history (yes; no)
- Prior limb revascularization (yes; no)
- History of heart failure (yes; no)

Statistical Analysis Plan

Protocol No.: **BAY 59-7939 / 17454**

Page: 20 of 36

- Diabetes mellitus(yes; no)
- Smoking status (former, never, current)
- Hypertension (yes; no)
- Hyperlipidemia (yes; no)
- Baseline (Month 1 visit)
 - ABI ≤ 0.80 or TBI ≤ 0.60 ;
 - ABI > 0.80 and TBI > 0.60 ;
 - TBI and ABI not done

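### Two subgroups listed as baseline (month-1 ABI/TBI and clopidogrel duration) are fixed only after randomisation but analysed from randomisation, and a single high ABI or TBI fits no level

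*SAP*

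**What the plan says.** SAP 6.2.4 opens with "The following subgroup analyses based on baseline and demographic characteristics are planned for the treatment comparisons of the primary efficacy and safety outcomes". Two items in the list concern us.

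- **ABI/TBI.** The item begins "Baseline (Month 1 visit" and has three levels: ABI ≤0.80 or TBI ≤0.60; ABI >0.80 and TBI >0.60; and "TBI and ABI not done".
- **Clopidogrel.** "Clopidogrel use continued after randomization" has the levels <30 days, ≥30 days and none.

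SAP 6.1.2 tabulates the same information differently. "Baseline Ankle Brachial Index (ABI) (at Month 1 visit" and "Baseline Toe Brachial Index (TBI) (at Month 1 visit" are two separate two-level variables, and the clopidogrel levels are none, ≤30 and >30 days.

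SAP 6.2.9 estimates a treatment hazard ratio within each level, on the analysis sets and data scopes of the main analyses. It covers the primary outcome, the secondary outcomes and their individual components, so CV death and all-cause mortality are included. SAP 6.4.5 does the same for TIMI major bleeding. On the scopes, SAP 4.5.2 says "The ITT data scope includes outcome events observed from randomization date until the ECOD" for efficacy and "The on-treatment data scope will include all outcome events observed from randomization until 2 days following permanent discontinuation of the study drug" for safety.

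Protocol 9.1 places Visit 1 one month after randomisation, ±10 days, and tolerates visits outside that window. Protocol 9.2.1.3 asks for ABI or, alternatively, TBI at each treatment visit.

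**The concern.** A subgroup level should be known when follow-up starts, and every patient should have exactly one. Neither holds here.

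The ABI/TBI level is unknown until about day 20 to 40, and a patient who dies first can only be placed in the not-done level. The 30-day clopidogrel split is unknown until day 30. A user who dies, or who stops because of an event, before then is placed in <30 days. Early events therefore help to decide the level in which they are counted.

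Separately, the upper ABI/TBI level needs both indices, although the visit schedule needs only one.

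At stake is the reading of some exploratory forest-plot rows. An apparent gradient in event rates could come from the classification rule, and one row leaves out patients who followed the schedule.

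**Working it through.** **1. The plan's own figure.** A daily-step model was run with the inputs of SAP 4.6: control hazard 7.5% per year, HR 0.80 on drug and 1 after discontinuation at the stated rates, 1.5% per year loss, 15/30/55% accrual over 18 months, and 24 months of further follow-up. It gives 1,014 events and 89.9% power, against the plan's 1,015 and 90%. The plan's flat rate is therefore a fair basis for counting early events.

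**2. Do the ABI/TBI levels cover everyone?** Each index can be low, above its cut-off or not done:

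| | TBI low | TBI above | TBI not done |
|---|---|---|---|
| ABI low | low | low | low |
| ABI above | low | not low | **no level** |
| ABI not done | low | **no level** | not done |

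Seven of nine patterns fit exactly one level and two fit none. Reading the last level as either index not done does not help, because a single low index would then fit two levels.

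If a share L of measured patients is truly low and a share u has one index only, independently, then (1−L)×u have no level. The documents give neither share. Assuming L = 30–70% and u = 25–90%, the result runs from 0.30×0.25 = 7.5% to 0.70×0.90 = 63%. With L = 50% it is 12.5–45%.

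**3. Deaths before Visit 1.** Expected deaths among 6,500 patients are 6,500×(1−exp(−m×d/365.25)). Taking m = 3–10% per year (assumed), this gives 11–35 by day 20, 16–53 by day 30 and 21–71 by day 40. None of these can enter a measured level.

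Suppose a flat hazard, Visit 1 at day 30 (0.0821 years), 2.3 years of follow-up and no true difference between levels. With m = 3% and 5% not done for other reasons:

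- not done: deaths 0.05×0.0667 + 0.95×0.00246 = 0.00567, over 0.111 patient-years, a rate of 5.1% per year;
- measured: deaths 0.0642, over 2.222 patient-years (per measured patient), a rate of 2.9% per year.

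The ratio is about 1.8. With 20% not done for other reasons it is about 1.2.

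**4. Hazard ratios within levels.** These come from an illustrative simulation. Assumptions: 2.6 years of follow-up, 35% of events fatal, 10% of ABI/TBI missing at random, 35% low (80% after a non-fatal month-1 event), no drug effect on ABI, and clopidogrel cut short only by death. Entries are ratios of event rates.

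| Setting | All | Low | Not low | Not done | <30 d | ≥30 d |
|---|---|---|---|---|---|---|
| Flat hazard, HR 0.80 | 0.80 | 0.80 | 0.80 | 0.79 | 0.80 | 0.80 |
| 3-fold hazard to day 30, HR 0.80 | 0.80 | 0.80 | 0.80 | 0.80 | 0.80 | 0.80 |
| 3-fold hazard and HR 0.60 to day 30, then 0.80 | 0.78 | 0.77 | 0.80 | 0.74 | 0.77 | 0.79 |

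Control rates per 100 patient-years (low, not low, not done) are 7.6, 7.3 and 8.5 in the first row and 8.4, 7.4 and 10.5 in the second. Rates by level move in every setting. Ratios move only in the third row, where the early effect differs.

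**5. Clopidogrel cut-point.** Protocol 8.1 describes a typical course of 30 days, and randomisation falls 0–10 days after the procedure. That leaves 30−10 = 20 to 30−0 = 30 days after randomisation. A course of exactly 30 days is ≤30 in 6.1.2 and ≥30 in 6.2.4. The SAP does not define the day count.

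**6. Cost of a landmark.** Primary events before day d are 3,250×(1−exp(−0.075×d/365.25)) + 3,250×(1−exp(−0.060×d/365.25)), with 0.060 = 0.80×0.075.

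- Day 30: 20.0 + 16.0, about 36 (3.5% of 1,015).
- Day 40: 26.6 + 21.3, about 48 (4.7%).
- Day 30 with a three-fold early hazard (assumed; 0.225 and 0.180): 59.5 + 47.7, about 107 (10.5%).

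**The case against.** The planned contrast is between treatments within a level, and survival to the label date applies to both arms. Step 4 bears this out: with a constant effect the ratios stay at 0.79–0.80. This part of the objection stands and limits the point.

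Neither variable is disguised, since both names state their timing. 6.2.4 also lists clopidogrel subgroups fixed at randomisation. 6.2.9 warns of spurious interactions and treats p<0.05 only as a flag. All this is true, but it does not change the time origin. The reason for a month-1 baseline in 6.2.7 concerns the change-from-baseline analysis of ABI and TBI. The landmark analyses in 6.2.8 and 6.4.5 are not tied to these subgroups.

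The intended low / not low / not done split is easy to guess, and a single-index rule may sit in the separate TLF specifications that the SAP mentions in its introduction. That is possible, but 6.2.4 points to no such rule, and its levels followed literally drop patients.

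A reader might infer that treatment, by changing the label, seriously biases these hazard ratios. The documents give no basis for a size. Suppose half the patients are low at twice the risk, and rivaroxaban moves 10 percentage points of patients from low to not low. The not-low ratio is then 0.80×(0.5×1+0.1×2)/0.6 = 0.93 if the moved patients keep the full low-level risk, but 0.80 if they take on the not-low risk.

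A reader might also blame the gap for a mismatch with the 6.1.2 table. That does not follow: two separate marginal tables would not determine a joint three-level row in any case.

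Finally, a landmark has a real cost, and Protocol 10.4 expects short- and intermediate-term events to be considerably more frequent than in its source data. This stands, and is why the landmark is proposed conditionally.

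**Conclusion.** The point holds as a minor one. Three facts rest on the text alone: two ABI/TBI patterns that the visit schedule allows have no level, both on the not-low side; both labels are set after randomisation but analysed from it, including for CV death and all-cause mortality; and the clopidogrel cut-point conflicts between two sections.

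Event rates by level are distorted as a result. Hazard ratios within levels are close to unaffected under a constant effect. They can be biased only if early and late effects differ or if treatment affects the label.

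The size cannot be derived, because the documents give no mortality, single-index or course-length shares. The 7.5–63% without a level and the rate ratio of 1.2–1.8 are ranges under stated assumptions, not estimates. The documents do not support reading this as a threat to the trial's conclusion: the analyses are descriptive, and the primary test, alpha and sample size are unaffected.

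**What to change.** In SAP 6.1.2, 6.2.4 and 6.2.9:

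- **(a)** Define low as any measured index at or below its cut-off, not low as all measured indices above, and not done as neither measured.
- **(b)** Use one clopidogrel cut-point and one stated day count in both sections.
- **(c)** Move both variables out of the baseline list, label them post-randomisation and exploratory, and keep the clopidogrel subgroups fixed at randomisation as the main ones.
- **(d)** If the two variables stay as time-to-event subgroups, start follow-up at a fixed landmark (day 30 for clopidogrel, day 40 for ABI/TBI, using measurements taken by then). Include patients alive, free of the analysed event and still in the data scope. State that this does not remove bias from a label that treatment affects.

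The eligibility ABI/TBI cannot stand in at these cut-offs, because inclusion criterion 2c makes every patient without prior limb revascularisation low.

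Items (a) to (c) cost wording and programming only. Item (d) loses the early events counted in step 6, discards ABI/TBI values taken after day 40, and describes only patients who reach the landmark.
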